## 7.7 Electrocardiogram (ECG)

The ECG assessment will measure PR Interval (msec), QRS Duration (msec), QT Interval (msec), QTcF Interval (msec), Heart Rate (bpm), and RR Interval (msec). The assessment will be done at the Screening visit (Visit 1), Visit 3 (Week 0), Visit 5 (Week 2), Visit 9 (Week 6), End of Treatment (Week 13, Visit 16) and Follow-Up (Visit 17). The interpretation of the results will be assessed as Normal or Abnormal, and any Abnormal results will be assessed for clinical significance. Ideally, the subject should be supine for at least 5 minutes before the first ECG is taken. If this cannot be done, this will be documented in the CRF. The ECG will be obtained as a continuous ECG of at least 50 ms. All readable ECGs of at least 10 ms will be interpreted by the central reader and reported.

Summary statistics for each ECG parameter and the change from baseline will be presented at each post-baseline visit. Additionally, summary statistics for the shifts in interpretation from baseline will be presented at each post-baseline visit. All ECG measurements will be presented in data listings.

### 7.8 Prior and Concomitant Medications

Prior and concomitant medication verbatim terms captured via the EDC system will be mapped to Anatomical/Therapeutic/Chemical (ATC) class and Preferred Names using the March 1, 2023 version of the World Health Organization (WHO) Drug Dictionary Enhanced available.

Prior medications are those medications started prior to and stopped before the first dose of study drug. Concomitant medications include: 1) medications started prior to, but still ongoing as of the first dose of study drug, 2) medications with a start date on or after first dose date. Prior and concomitant medications will be summarized separately by WHO ATC class and preferred name. These summaries will present the number and percent of subjects using each medication. Subjects may have more than one medication per ATC class and preferred name. At each level of subject summarization, a subject is counted once if one or more medications at that level is reported for the subject. The drug classification will be the ATC classification 4. If this classification is not present, the next available classification will be utilized. Medications taken with a frequency of PRN or "as needed" will be excluded from the tabular summaries. Each summary will be ordered by descending order of incidence of ATC class and preferred term.

## 7.9 Monthly Seizure Episodes

Monthly seizure frequency will be derived as defined in Section 5.3. Seizure frequency will be assessed from a seizure log that is part of the Caregiver Diary which is completed daily by the caregiver.

Summary statistics on the observed and the change from baseline in monthly seizures will be displayed at baseline and end of treatment. Within subject changes will be assessed using a Wilcoxon Signed Rank Test.

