Seizures present another challenge for 30%-51% of individuals with PTHS. ^{4, 6, 8-11, 13, 15} The range of seizure types includes generalized tonic-clonic, atonic, focal onset, and infantile spasms. ^{6, 8, 10, 16-18} Additionally, between 18%-42% of individuals with PTHS experience some type of sleep disturbance, typically insomnia or night awakenings. ^{6, 8}

Individuals with PTHS face a range of behavioral challenges.^{3, 4, 6-8, 10} Compared to Angelman Syndrome (AS) and Cornelia de Lange syndrome (CdLS), other genetically based disorders with similar early signs and features, the behavioral phenotype of PTHS is particularly characterized by the following: 1) a high level of Autism Spectrum Disorder (ASD) symptomatology 2) social communication difficulties, 3) atypical sensory processing, and 4) high levels of physical aggression and self-injury.¹³ Aggression and aggressive behavior are observed in 40%-54% of individuals,^{8, 11-13} and in 38% of individuals, this has included destruction of property.¹³ Between 60-71% of individuals demonstrate self-injurious behaviors.^{6, 9, 11} Anxiety (81%) and agitation (88%) are also common symptoms.⁶

Up to 95% of individuals met the cut off score for possible ASD on the Social Communication Questionnaire (SCQ) screener for ASD. ¹³ Individuals have also been shown to score high on the Autism Diagnostic Interview measure. ¹² On the SCQ, they demonstrated more problems with communication and reciprocal social interaction than individuals with AS. They also showed lower sociability with both

familiar and unfamiliar people compared to individuals with AS, and with familiar people compared to individuals with CdLS. ¹³ Individuals with PTHS also have atypical sensory processing. In response to behaviors in social contexts, the majority of individuals are hyporesponsive, but are hyperresponsive to sensory input. ¹³

Stereotypic behaviors are highly prevalent (54%-94%)^{3,6,8,10,12,13} and include object stereotypy,^{3,13} body stereotypies such as body rocking (54%-78%) and hand and finger stereotypies (48-85%) including clapping, flapping (up to 80%), hand-wringing/hand-washing (45%), hand mouthing or biting (54%), finger movements (54%), and wrist movements (45%).^{6-9,12,13} Head shaking and head banging have also been reported.^{6,9}

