# 5 Statistical Methods

The statistical analyses will be reported using summary tables, listings, and figures (TLFs). Numbering for TLFs will be based on the recommended numbering convention provided by the International Conference on Harmonization (ICH).

The analyses described in this plan are considered *a priori*, in that they have been defined prior to database lock. Any analysis added after the database lock will be considered

exploratory. Post hoc analyses will be labeled as such on the output and identified in the CSR.

Unless noted otherwise, all statistical tests will be two-sided with a significance level of  $\alpha$  = 0.05 and descriptive in nature. Continuous variables will be summarized with means, standard deviations, medians, minimums, and maximums. Categorical variables will be summarized by counts and percent of subjects in corresponding categories. Missing values are not considered for percent calculations, unless stated otherwise. Footnotes may be used to specify the percent calculation as appropriate. Baseline for all analyses is defined in Section 5.2.3.

Individual subject data obtained via the electronic data capture (EDC) system and from external vendors (excluding PK data) will be presented in listings.

All analyses and tabulations will be performed using SAS version 9.4 or higher. Tables, listings, and figures will be presented in portable document format (PDF) and in Rich Text Format (RTF). All analyses will be subject to formal verification procedures. Specifically, results will be verified by independent programming. All documents will be reviewed by the lead statistician to ensure accuracy and consistency of analyses. The validation process will be used to confirm that statistically valid methods have been implemented and that all data manipulations and calculations are accurate. Checks will be made to ensure accuracy, consistency with this plan, consistency within tables and consistency between tables and corresponding data listings.

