## 7 Safety Analysis

The primary objective of the study is to investigate the safety, tolerability, and pharmacokinetics of treatment with NNZ-2591 in children and adolescents with PTHS.

All safety analyses will be based on the Safety Population.

Safety will be assessed based on incidence of treatment emergent adverse events (TEAEs), serious adverse events (SAEs), changes in vital signs, changes in laboratory measures, neurological, ophthalmological, and physical exam results, and changes in ECG's.

Tolerability will be assessed based on daily dosing logs, requiring dosing adjustments or discontinuations, dosing compliance, and AEs related to subject experience.

Pharmacokinetics will be summarized separately outside of this SAP.

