## 7.10 Monthly Major Breathing Episodes

Monthly frequency of major breathing events will be derived as defined in Section 5.3. Breathing event frequency will be assessed from a Major Respiratory Events log that is part of the Caregiver Diary which is completed daily by the caregiver.

Summary statistics on the observed and the change from baseline in monthly breathing episodes will be displayed at baseline and end of treatment. Within subject changes will be assessed using a Wilcoxon Signed Rank Test.

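### The SAP 7.9 seizure table pools all dosed children, so its signed-rank p-value often cannot fall below 0.05 and its median change is often zero; add a table of children with seizures and a count of those who worsen

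*SAP*

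**What the plan says.** SAP 7.9 (Monthly Seizure Episodes) has two outputs. The first is descriptive: "Summary statistics on the observed and the change from baseline in monthly seizures will be displayed at baseline and end of treatment". The second is the test: "Within subject changes will be assessed using a Wilcoxon Signed Rank Test". SAP 7.10 gives major breathing episodes the same treatment.

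The analysis set is everyone dosed: "All safety analyses will be based on the Safety Population". Nothing in 7.9 limits the table to children who have seizures, says how zero changes are handled, counts children who worsen, or gives an interval. The SAP addendum does not change 7.9.

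SAP 5 sets the general rules. On tests: "Unless noted otherwise, all statistical tests will be two-sided with a significance level of" "0.05 and descriptive in nature". On summaries: "Continuous variables will be summarized with means, standard deviations, medians, minimums, and maximums".

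Protocol 5.1 gives the background rate: "Seizures present another challenge for 30%-51% of individuals with PTHS". Protocol 7.1 and SAP 2.2 plan about 10 to 20 participants.

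**The concern.** Section 7.9 sits in the safety chapter, where the natural question is whether seizures get worse on treatment. About half or more of the children are expected to have no seizures in either period. Their change is zero, so the signed-rank test ignores them and the median is pulled to zero by them.

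A table showing a zero median change and p above 0.05 could then be read as no effect on seizures when the number of informative children was too small for the test to say anything else. The section has no output that tells the reader how much worsening remains possible. The SAP nowhere says that p above 0.05 means no harm; the risk lies in how the table would be read when the next trial is planned.

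**Working it through.** **The plan's own figure.** No power or precision is stated for seizures. The only signed-rank calculation is for CGI-I (SAP 5.1): n = 10, effect size 1.24, power 0.90. Using a noncentral t with efficiency 3/π and effective n rounded down (10 × 3/π = 9.5, so 9), power is 0.901, which agrees. For n = 20 (effective n 19) the stated differences give 0.807, 0.851 and 0.899 against 0.80, 0.85 and 0.90. Those figures assume that every child contributes a non-zero change, so they do not carry over to seizures.

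**Floor of the p-value.** With m non-zero changes all in one direction, the smallest exact two-sided p is 2/2^m. For m = 5 this is 2/32 = 0.0625; for m = 6 it is 2/64 = 0.031. At least six non-zero changes are needed.

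**Number of informative children.** Take X ~ Binomial(n, prevalence), with n = 10 or 20 and prevalence 30% to 51%. The 40% column is an intermediate value. Expected X runs from 10 × 0.30 = 3 to 20 × 0.51 = 10.2.

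**Zero median.** Suppose every affected child worsens and all others stay at zero. With even n the median is exactly zero when X ≤ n/2 − 1.

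| | 30% | 40% | 51% |
|---|---|---|---|
| n = 10: P(X ≤ 5), p < 0.05 impossible | 95% | 83% | 60% |
| n = 20: P(X ≤ 5), p < 0.05 impossible | 42% | 13% | 2% |
| n = 10: P(X ≤ 4), median change zero | 85% | 63% | 35% |
| n = 20: P(X ≤ 9), median change zero | 95% | 76% | 38% |

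The zero median is more likely than not only below about 45% prevalence at n = 10 and 48% at n = 20.

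**Sensitivity.**
- The 30% to 51% is general prevalence, not the share with a seizure in the diary windows. If 20% seize during the study, the test is blocked in 99% (n = 10) or 80% (n = 20) of trials. New-onset seizures would work the other way.
- SAP 7.9 does not say the test is exact; Protocol 11.3 specifies an exact level for efficacy. A normal approximation without continuity correction gives p = 0.043 at m = 5, so the floor moves by one child. The blocked share is then P(X ≤ 4): 85% to 35% at n = 10 and 24% to 0.5% at n = 20 for 30% to 51%.

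**What a clean result would exclude.** The exact two-sided 95% upper limit for 0 of k is 1 − 0.025^(1/k). For 0 of 5 it is 52%; for 0 of 10 it is 31%.

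**Breathing (7.10).** Protocol 5.1 gives 45% to 86%. P(X ≤ 5) is 74% to 0.7% at n = 10 and at most 6% at n = 20, so the problem is milder.

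**The case against.** The strongest reply is that 7.9 is one of several routes to a seizure signal, and that no decision depends on its p-value. Most of this stands.

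- SAP 5 calls the tests descriptive and also requires means, minimums and maximums. A reader might infer that the table would look the same if seizures doubled. The documents do not support that: the mean and maximum can move, although one child with frequent seizures can dominate a mean at this size.
- A reader might also infer that seizure safety rests on this test. It does not. Protocol 10.6 requires a baseline symptom that worsens after dosing to be recorded as an adverse event, Protocol 10.1 includes increased frequency, SAP 7.2 tabulates treatment-emergent events, the investigator reviews the diary (Protocol 9.5.10), and the DSMC receives raw listings (SAP 4).
- It is tempting to quote the chance of missing a true doubling. That figure depends on an assumed level of noise with no source in the documents. At n = 20 and 51% prevalence it falls from about 69% under heavy period-to-period variation to 8% under pure Poisson counts, so it is not relied on here.
- Protocol 7.1 allows extra enrolment to reach about 20 completers, where blocking is 42% at most over the quoted prevalence range.

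The reply does not remove the arithmetic. Adverse event tables depend on an investigator recording an exacerbation. Section 7.9 is where diary frequency is quantified, and its only inferential output may be unable to signal worsening.

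**Conclusion.** The point holds as a limit on the 7.9 table. At n = 10 the exact test is blocked more often than not across the quoted prevalence range (95% to 60%); at n = 20 it is a substantial risk at 30% (42%) and negligible at 51% (2%). A zero median despite universal worsening among affected children is common at low to middle prevalence, but not at 51%, so it cannot be called usual over the whole range.

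These results assume an exact test, independent children, and the protocol's general prevalence as the share with seizures during the study. They need no model of seizure rates. They do not show that a seizure signal would be missed by the safety assessment as a whole. The change is worth making because it is cheap and states plainly how little a handful of children can exclude.

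**What to change.** In SAP 7.9, and with less need in 7.10, add a table restricted to children with at least one event in the screening/baseline or treatment period:

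- each child's baseline and on-treatment monthly rate, and the absolute change;
- the number whose rate rises, and the number whose rate rises by a pre-stated amount, each with an exact 95% confidence interval;
- children with no baseline events counted separately as new onset, because a ratio is undefined for them.

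Keep the all-children summary and the signed-rank p-value as descriptive. Add a footnote giving the number of non-zero changes and stating that p above 0.05 does not exclude worsening: 0 of 5 children worsening still allows up to 52%, and 0 of 10 up to 31%. Restricting the population alone would repair the median but not the p-value floor.

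Before any rate is computed, reconcile the seizure definition in SAP 5.3. As written, it divides treatment-period seizures by the screening/baseline duration, whereas the parallel breathing definition uses treatment duration. With 91 treatment days and a 28- to 42-day baseline, the on-treatment rate would be inflated 3.25-fold (91/28) to 2.2-fold (91/42).

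The cost is SAP wording and one small table per section from diary data already collected. The intervals will be wide, and some children will cross any threshold by chance. For illustration, under one assumed heavy-noise model 33% of affected children show an observed doubling with no drug effect, so among five the chance of at least one is 1 − 0.67^5 = 86%. The threshold count should therefore be read as descriptive.

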## 7.10 Monthly Major Breathing Episodes

Monthly frequency of major breathing events will be derived as defined in Section 5.3. Breathing event frequency will be assessed from a Major Respiratory Events log that is part of the Caregiver Diary which is completed daily by the caregiver.

Summary statistics on the observed and the change from baseline in monthly breathing episodes will be displayed at baseline and end of treatment. Within subject changes will be assessed using a Wilcoxon Signed Rank Test.

# 8 Efficacy Analysis

The secondary objective is to investigate measures of efficacy during treatment with NNZ-2591 Oral Solution in children and adolescents with PTHS.

All efficacy analyses will be conducted on the ITT and mITT populations.

### 8.1 Efficacy Variables

There are no primary efficacy variables.

Secondary variables for efficacy to be considered include:

- PTHS-specific Clinical Global Impression Scale–Overall Improvement (CGI-I) Score
- PTHS-specific Clinical Global Impression Scale–Domain Improvement Scores
- Clinical Global Impression Scale Severity (CGI-S) Overall Severity Score
- Clinical Global Impression Scale Severity (CGI-S) Domain Severity Scores
- MacArthur-Bates Communicative Development Inventory (MB-CDI) Scores
- Observer-Reported Communication Ability (ORCA) Score
- Caregiver Top 3 Concerns Likert Scale Scores

- Aberrant Behavior Checklist-2 (ABC-2) Scores
- Behavior Problems Inventory-Short Form (BPI-SF) Scores
- Child Sleep Habits Questionnaire (CSHQ) Scores
- Gastrointestinal Health Questionnaire (GIHQ) Scores
- Caregiver Impression of Change Scores
- Vineland Adaptive Behavior Scales-3 Scores
- Quality of Life Inventory-Disability (QI-Disability) Scores
- Impact of Childhood Neurological Disability (ICND) Overall quality of life rating
- Modified Two-minute walk test (2MWT) total distance
- SB5 raw, z-deviation, age-equivalent, and Change Sensitive scores or BSID-4 scores (raw, GSV, age-equivalent; standard and scaled scores may be assessed for participants for whom the standard scores can be calculated)

Biomarker variables and gut microbiome analyses will be described in a separate analysis plan.

## 8.2 Adjustments for Covariates

A list of potential covariates to be used in descriptive summaries or analyses are provided below.

- Age at Baseline
- Sex (Male, Female)
- SB5 NVIQ or BSID-4 NVDQ at Baseline
- History of developmental regression (yes, no)
- ASD diagnosis (yes, no)
- CGI-S Overall Score at Baseline

## 8.3 Examination of Subgroups

No subgroup analyses are planned.

### 8.4 Multicenter Studies

All sites will be pooled for this analysis.

## 8.5 Multiplicity Comparison/Multiplicity

No formal statistical analysis is planned; therefore, there will be no adjustments for multiplicity.

### 9 Efficacy Analysis Methods

#### 9.1 Primary Efficacy Analysis

There is no primary efficacy endpoint.

#### 9.2 Secondary Efficacy Analysis

The efficacy endpoints will be analyzed using a Wilcoxon signed rank test on the paired subject data from baseline to end of treatment (Visit 16) and Visit 9 (Week 6) when applicable. Descriptive statistics will be used to summarize the data. For total scores (and certain subscale score as defined below) waterfall plots and histograms or bar charts (as appropriate) will also be created at the End of Treatment (EOT) visit with plots for all subjects and separate plots indicating each of the following: age groups, NVIQ/DQ score (>= 50, < 50), sex (Male, Female) and number of concomitant medications  $(> 6, \le 6)$ . The number of concomitant medications will be determined as defined in Section 5.3. Line graphs plotting scores by visit will also be generated for the mean group data and showing individual participants. The NVIO/DO score is the SB5 Non-Verbal Intelligence Quotient (z-deviation), or the BSID-4 Non-verbal Developmental Quotient depending on which assessment the subject took. The number and percentage of subjects who had an IQ/DQ score  $\geq 50$  and < 50 at Baseline and End of Treatment will be presented in a table for NVIQ/DQ, VIQ/DQ, and FSIQ/Overall DQ. For assessments that use discrete scores, the histograms will be changed to bar charts. If the change from baseline of the discrete scores is presented, then the change from baseline value will be rounded using conventional rounding standards for ease of presentation and understanding in the bar chart. For scales with domain scores, forest plots displaying the mean change from baseline and 95% CI for each domain score at EOT will be generated. All figures will be generated on the ITT and mITT populations.

Exploratory analyses on some endpoints using linear regression may be performed to assess the relationship between treatment and specified covariates or combinations of covariates. The empirical cumulative distribution function will be plotted for certain variables. As appropriate, collective response analysis may be done to assess data across subjects.

A correlation analysis of the efficacy measures will be done using Pearson correlation coefficients at Baseline and EOT. The correlation of each total score will be measured against the others and presented in a table and a heat map/matrix. CGI-I and CGI-S domain scores will also be included in the correlation analysis. Test-retest reliability will be assessed for continuous efficacy assessments collected more than once during the Screening period (Visits 1, 2, and 3, pre-dosing) using Intraclass Correlation Coefficients

Statistical Analysis Plan 30APR2024

(ICC). The ICC will be based on covariance parameter estimates from a Restricted Maximum Likelihood Mixed Model including results from assessments conducted during the Screening/Baseline period with a random effect for subject. The ICC will be derived as: ICC = Within-subject covariance/Total covariance. ICC values range from 0 to 1, with values closer to 1 indicating greater test-retest reliability.

A treatment policy estimand will be used for all endpoints. The variables of interest are numeric scores associated with subject responses. Summaries will be performed on the observed data. There will be no imputations for completely missing scores or intercurrent events. Handling of missing responses items that contribute to total and subscale scores are defined in Section 5.2.5.

Results for each efficacy variable will also be listed by subject.

#### 9.2.1 Clinical Global Impression Scale - Overall Improvement Score

CGI-I assessments are completed at Visit 9 (Week 6), End of Treatment (Week 13, Visit 16), and Follow-up (Visit 17). The clinician rates how much the subject's illness has improved or worsened relative to Visit 3 (Week 0). The Overall CGI-I score is rated on a 7-point scale, where 1='very much improved'; 2='much improved'; 3='minimally improved'; 4='no change'; 5='minimally worse'; 6='much worse'; 7='very much worse'. Scores of 1, 2, and 3 indicate improvement. Within subject change is indicated by the score at each relevant follow-up visit (Week 6, Visit 9 and Week 13, EOT, Visit 16). If an overall score is missing, that subject will be excluded from analysis at that visit.

Summary statistics for the CGI-I Overall score will be displayed at all post-baseline visits. Within subject changes will be analyzed using a Wilcoxon signed rank test at EOT and Week 6. The overall score will be presented in figures as described in Section 9.2. As this score is categorical, the waterfall plots will be adjusted so a score of "7 – Very Much Worse" will be presented at the bottom of the graph and a score of "1 – Very Much Improved" will be presented at the top of the graph. The overall score will also be presented as a line graph at post-baseline visits.

